5.1.1.2 Spinal Hematoma

Post-lumbar puncture spinal hematoma is a very rare but important potential risk that can present as persistent back pain, radicular pain, new sensory or motor symptoms, sphincter disturbance, or meningism. Prompt MRI scanning should be performed if suspicion of spinal hematoma arises. Patients with susceptibility to bleeding, patients with coagulopathy, and patients receiving anticoagulant therapy are at an increased risk of spinal hematoma and will be excluded from the study (see Section 4.1.2).

Management of spinal hematomas should include consultation with neurosurgical colleagues.

5.1.1.3 Meningitis

Meningitis is a rare potential risk of LP. Patients may present with headache, meningism, photophobia, neck stiffness, and pyrexia. Guidelines for management of patients with suspected meningitis are provided in Table 2.

5.1.2 Potential Risks Associated with RO7234292

The potential risks identified below have been considered in relation to clinical data available as of 07 August 2020, including the completed Phase I/IIa study and its Phase II OLE Study (BN40697), Study BN40423 (ODC), and the ongoing Study BN40955.

5.1.2.1 Neurologic Changes

In cynomolgus monkeys, acute, transient deficits in lower spinal reflexes (patellar reflex in particular) were typically observed 2–8 hours following dosing, in the 13-week and the chronic toxicity studies. The transient changes in patellar reflex were observed in all treatment groups, including controls, with a slightly higher incidence in the high-dose groups. These findings were fully reversible within 24 hours following dosing. No other treatment-related changes in general sensory and motor function parameters nor changes in the cerebral reflexes were observed.

In the Phase I/IIa multiple ascending dose (MAD) study (ISIS 443139-CS1), no adverse trends in neurological examinations were detected and only a few drug-related neurological AEs were observed in ≥ 2 patients. See the RO7234292 Investigator's Brochure for more information.

In the other completed and ongoing studies, among events associated with peripheral nervous system, 2 cases of asymptomatic lumbar radiculopathy that were characterized by loss of ankle reflexes without changes in motor or sensory function and one serious adverse event (SAE) of radiculopathy and hyporeflexia (Suspected Unexpected Serious Adverse Reaction [SUSAR] case) have been observed in the Phase II OLE Study

BN40697 at the Q4W 120 mg cohort. In Study BN40423 ODC, one case of lumbar radiculopathy (post traumatic, considered not related to study drug by the investigator) was reported in the Q8W cohort. In Study BN40955, no treatment-emergent radiculopathy cases have been reported.

Among reflex change events in Study BN40697, areflexia and reflexes abnormal were reported in 1 patient each in the Q4W cohort and hyporeflexia was reported in 1 patient each in the Q4W and Q8W cohorts, respectively. In Study BN40955, treatment-emergent areflexia was reported in 1 patient in the Q8W cohort, and none were reported in the Q16W cohort. No reflex change AEs have been reported in Study BN40423 ODC. For details, see the RO7234292 Investigator's Brochure.

Among events associated with the central nervous system in Study BN40697, dysarthria was reported in 2 patients in the Q4W cohort; coordination abnormal was reported in 1 patient in the Q4W cohort; pleocytosis was reported in 1 patient in the Q4W arm; and ataxia was reported in 1 patient each in the Q4W and Q8W cohorts, respectively. An SAE of cerebrovascular accident was reported in 1 patient in the Q4W cohort, which was considered not related to study drug by the investigator. SAEs of hemiparesis, myelitis, and neuritis (SUSAR cases) were reported in another patient in the Q4W cohort. In Study BN40423 ODC, ataxia (SUSAR case) and dysarthria were reported in 1 patient each in the Q4W cohort. In Study BN40955, treatment-emergent event of ataxia was reported in 1 patient each in the Q8W and Q16W cohorts, respectively, pleocytosis was reported in 1 patient in the Q8W cohort, and two neurological SUSAR cases were reported in 2 patients in the Q8W cohort (1 patient each for arachnoiditis and aseptic meningitis). For details see the RO7234292 Investigator's Brochure. Following LP administration and post-LP mobilization, neurologic examinations should be conducted. In addition, patients should be observed in-clinic for any complications or complaints post-LP and IT bolus injection of RO7234292.

5.1.2.2 Elevations in CSF WBCs and Protein

The CSF WBC elevations were also observed in the chronic non-human primate study with slight increases over time. Increases were mild, and there was no apparent dose dependency.

CSF protein and WBC increases have been observed in the RO7234292 program.

In Study BN40697, one patient was diagnosed with chemical meningitis (SUSAR case) in the Q4W cohort. As of 04 October 2020, in the ongoing Study BN40955, one patient experienced aseptic meningitis (clinically not infectious) and one patient experienced arachnoiditis, in the Q8W cohort.

For details on CSF proteins and WBC laboratory values and non-serious AEs of CSF WBC and protein increases, please refer to the RO7234292 Investigator's Brochure.

5.1.2.3 Thrombocytopenia

Reductions in platelet count have been observed after systemic administration of some 2'-MOE chimeric ASOs to clinical trial subjects. However, no clinically significant reductions in platelet counts have been observed in clinical studies for RO7234292 to date. In one 13-week and one 9-month IT toxicity studies of RO7234292 in the cynomolgus monkey, there were no effects on hematology or coagulation parameters.

No clinically significant reduction in platelet counts *has been observed in the completed and ongoing studies in the RO7234292 program to date.*

Platelet counts will be monitored at each study visit prior to LP. See [Table 2](#) for patient stopping and treatment discontinuation rules.

5.1.2.8 Potential Risk due to Reduction of Target Protein HTT

By specifically targeting mRNA from both *HTT* alleles, RO7234292 lowers levels of both mHTT protein and normal wild-type huntingtin (wtHTT) protein in all patients, regardless of genetic variations. The ASO modality provides partial, transient, reversible, and titratable HTT lowering. Partial HTT lowering is safe and well tolerated in normal rodents and non-human primates, as shown in multiple studies using ASOs and non-reversible approaches. Furthermore, no safety signals of concern emerged during the completed Phase I/IIa study of RO7234292 in adults with HD (see RO7234292 Investigator's Brochure), in which partial lowering was achieved.

Transgenic mice expressing human mHTT develop progressive HD-like phenotypes that recapitulate many aspects of HD in humans. Antisense oligonucleotide-mediated mHTT lowering provides therapeutic benefits and often restores normal functioning in transgenic and fully humanized animal models of HD, with generally similar results

regardless of whether wtHTT is also lowered. Moreover, no detrimental effects of partial wtHTT lowering in animal models have been reported in multiple studies using ASOs and non-reversible approaches.

Still, the current understanding of the diverse cellular functions of HTT suggests potential theoretical risks associated with reducing total HTT levels in people with HD. More than two decades of research findings implicate HTT in a wide array of cellular functions, including microtubule-based transport, F-actin-based trafficking, Rab-based trafficking, brain-derived neurotrophic factor transport, ciliogenesis, transcription, chromatin modification, post-transcriptional gene-expression regulation, neurogenesis, synaptogenesis, synaptic plasticity, signaling pathways, cell stress responses, cell survival, selective macro-autophagy and DNA damage repair, as detailed in a recent review article (Liu and Zeitlin 2017).

Although functional HTT (mutant or wild-type) is essential for embryogenesis, near-complete genetic ablation of HTT has little or no reported neurological effect in normal adult animals. However, complete ablation of wtHTT protein expression throughout life results in a worsening motor phenotype and, in male transgenic mice, age-dependent emergence of brain atrophy and decreased testicular size (Van Raamsdonk et al. 2005). In contrast, decreases in mHTT protein expression ameliorate disease, and increases in mHTT protein exacerbate disease in animal models of HD, regardless of concomitant changes in wtHTT protein levels.

No clinically significant new neurologic events were observed in the completed Phase I/IIa study. As a precaution, a full neurologic examination will be conducted at each study visit (on dosing days before and after dosing), and additional monitoring of cognition will be conducted throughout the study using the MoCA.

5.1.3 Management of Patients who Experience Adverse Events

5.1.3.1 Dose Modifications

No dose modifications are permitted in this study, whether by varying the amount of study drug volume injected or the frequency of procedure per protocol (i.e., all participants will receive 20 mL of study drug at every study drug administration either on a Q8W or Q16W basis as assigned by IxRS).

5.1.3.2 Treatment Interruption

Study drug may be temporarily suspended in patients who experience toxicity considered to be related to study drug. If study drug has been withheld for >60 days from the date of the first missed dose, because of signs of persistent drug-induced toxicity or if the scheduled dose has been missed, the investigator should consult the Medical Monitor to determine if discontinuation from study drug is warranted. Study drug may be suspended for reasons other than toxicity (e.g., surgical procedures) with Medical Monitor approval. The investigator and the Medical Monitor will determine the acceptable length of treatment interruption.

5.1.3.3 Management Guidelines

Guidelines for management of specific AEs are outlined in [Table 2](#). Additional guidelines are provided in the subsections below.

Initial clinical laboratory tests with results meeting criteria for withholding study drug must be repeated on new specimens as soon as possible, and results must be available prior to administering the next dose of study drug. In general, patients who do not reach the stopping rule may continue dosing; however, the investigator and Sponsor should confer as to whether additional close monitoring of the patient is indicated.

Table 2 Guidelines for Management of Patients Who Experience Adverse Events

Event	Action to Be Taken

Elevations in CSF WBC count or proteins or suspected meningitis, radiculitis, arachnoiditis, hydrocephalus, or other acute neurologic symptoms
	
 • Withhold study drug if diagnosis of meningitis, radiculitis, arachnoiditis, hydrocephalus, or acute neurologic symptoms is suspected and initiate appropriate diagnostic work-up as indicated. • Clinical signs and symptoms of hydrocephalus (e.g., new onset of persistent or worsening gait disturbance, change in level of consciousness/cognition, changes in continence, or a combination of all 3 signs) are required for diagnosis of suspected hydrocephalus. • Clinical signs and symptoms of meningitis (e.g., headache, stiff neck, fever) plus confirmatory WBC count are required for diagnosis of suspected meningitis; and clinical signs and symptoms are required for diagnosis of radiculitis, arachnoiditis, or acute neurologic symptoms. Isolated low-level (e.g., 5–50 μL WBC count) elevations in CSF WBC count without clinical symptoms does not meet criteria for diagnosis of suspected meningitis. • The Medical Monitor should be consulted in all cases where CSF WBC count elevations above 10/μL are present, or a change from baseline in CSF proteins greater than 2\times baseline or where there is uncertainty to discuss next steps of patient management in the study. • If diagnosis of suspected meningitis, radiculitis, arachnoiditis, hydrocephalus, or other acute neurologic symptoms is refuted, the study drug may be resumed after consultation with the Medical Monitor. • In the event meningitis, radiculitis, arachnoiditis, hydrocephalus, or acute neurologic symptom diagnosis is confirmed, standard of care therapies should be instituted as indicated.

Table 2 Guidelines for Management of Patients Who Experience Adverse Events (cont.)

Event	Action to Be Taken
Thrombocytopenia	
 • If platelet count is $\leq 100,000/\text{mm}^3$: 
 – Monitor platelet count weekly. • If platelet count is $\leq 75,000/\text{mm}^3$ and $> 50,000/\text{mm}^3$ in the absence of major bleeding or clinically relevant non-major bleeding: 
 – Withhold study drug until the platelet count has recovered to $> 100,000/\text{mm}^3$. – The suitability of the patient for continued dosing and frequency of monitoring should be discussed with the Medical Monitor. • If platelet count is $\leq 50,000/\text{mm}^3$: 
 – Permanently discontinue study drug. – Monitor platelet counts daily until two successive values show improvement. Then monitor every 2–3 days until platelet count is stable, and at least weekly until platelet count returns to normal. • Treatment per standard of care should be considered for patients whose platelet count is $< 25,000/\text{mm}^3$.

Table 2 Guidelines for Management of Patients Who Experience Adverse Events (cont.)

Event	Action to Be Taken
Decreased renal function	
 • Withhold study drug in the event of a persistent (>2 weeks) decrease in eGFR or CrCl or increase in creatinine, as defined below: 
 – eGFR or CrCl (using Cockcroft-Gault) <60 mL/min. – Creatinine level increase of 2.0× above baseline. – Study drug may be resumed when follow-up test results show that the patient no longer meets the dose interruption criteria.
Elevated liver enzymes	
 • ALT or AST is >3×ULN: 
 – Monitor weekly until ALT and AST return to ≤1.2×ULN. – Further investigation into the liver enzyme elevations may include hepatitis serologies and other diagnostic tests at the discretion of the investigator in consultation with the Medical Monitor. • Withhold study drug in the event of liver enzymes that meet the following criteria without an alternative explanation (as discussed with the Medical Monitor): 
 – ALT or AST >5×ULN. – ALT or AST >3×ULN, combined with total bilirubin >2× ULN or INR >1.5. – ALT or AST >3× ULN coinciding with new appearance of fatigue, nausea, vomiting, right upper quadrant pain or tenderness, fever, rash, and/or concomitant eosinophilia. – Discontinue study drug permanently if levels do not return to baseline after 30 days.

CrCl=creatinine clearance; CSF=cerebrospinal fluid; eGFR=estimated glomerular filtration rate; ULN=upper limit of normal.

5.2 SAFETY PARAMETERS AND DEFINITIONS

Safety assessments will consist of monitoring and recording AEs, including serious adverse events (SAEs) and adverse events of special interest (AESIs), performing protocol-specified safety laboratory assessments, measuring protocol-specified vital signs, and conducting other protocol-specified tests that are deemed critical to the safety evaluation of the study.

Certain types of events require immediate reporting to the Sponsor, as outlined in Section 5.4.

5.2.1 Adverse Events

According to the ICH guideline for Good Clinical Practice, an AE is any untoward medical occurrence in a clinical investigation subject administered a pharmaceutical product, regardless of causal attribution. An AE can therefore be any of the following:

- Any unfavorable and unintended sign (including an abnormal laboratory finding), symptom, or disease temporally associated with the use of a medicinal product, whether or not considered related to the medicinal product
- Any new disease or exacerbation of an existing disease (a worsening in the character, frequency, or severity of a known condition) (see Sections [5.3.5.9](#) and [5.3.5.10](#) for more information)
- Recurrence of an intermittent medical condition (e.g., headache) not present at baseline
- Any deterioration in a laboratory value or other clinical test (e.g., ECG, X-ray) that is associated with symptoms or leads to a change in study treatment or concomitant treatment or discontinuation from study drug
- Adverse events that are related to a protocol-mandated intervention, including those that occur prior to assignment of study treatment (e.g., screening invasive procedures such as biopsies)

5.2.2 Serious Adverse Events (Immediately Reportable to the Sponsor)

A SAE is any AE that meets any of the following criteria:

- Is fatal (i.e., the AE actually causes or leads to death)
- Is life-threatening (i.e., the AE, in the view of the investigator, places the patient at immediate risk of death)
 - This does not include any AE that, had it occurred in a more severe form or was allowed to continue, might have caused death.
- Requires or prolongs inpatient hospitalization (see Section [5.3.5.11](#))
- Results in persistent or significant disability/incapacity (i.e., the AE results in substantial disruption of the patient's ability to conduct normal life functions)
- Is a congenital anomaly/birth defect in a neonate/infant born to a mother exposed to study drug
- Is a significant medical event in the investigator's judgment (e.g., may jeopardize the patient or may require medical/surgical intervention to prevent one of the outcomes listed above)

The terms "severe" and "serious" are not synonymous. Severity refers to the intensity of an AE (e.g., rated as mild, moderate, or severe, or according to National Cancer Institute Common Terminology Criteria for Adverse Events [NCI CTCAE]; see Section [5.3.3](#)); the event itself may be of relatively minor medical significance (such as severe headache without any further findings).

Severity and seriousness need to be independently assessed for each AE recorded on the eCRF.

Serious adverse events are required to be reported by the investigator to the Sponsor immediately (i.e., no more than 24 hours after learning of the event; see Section 5.4.2 for reporting instructions).

5.2.3 Adverse Events of Special Interest (Immediately Reportable to the Sponsor)

Adverse events of special interest are required to be reported by the investigator to the Sponsor immediately (i.e., no more than 24 hours after learning of the event; see Section 5.4.2 for reporting instructions). Adverse events of special interest for this study are as follows:

- Cases of potential drug-induced liver injury that include an elevated ALT or AST in combination with either an elevated bilirubin or clinical jaundice, as defined by Hy's Law (see Section 5.3.5.7)
- Suspected transmission of an infectious agent by the study drug, as defined below:
Any organism, virus, or infectious particle (e.g., prion protein transmitting transmissible spongiform encephalopathy), pathogenic or non-pathogenic, is considered an infectious agent. A transmission of an infectious agent may be suspected from clinical symptoms or laboratory findings that indicate an infection in a patient exposed to a medicinal product. This term applies only when a contamination of the study drug is suspected.

5.3 METHODS AND TIMING FOR CAPTURING AND ASSESSING SAFETY PARAMETERS

The investigator is responsible for ensuring that all AEs (see Section 5.2.1 for definition) are recorded on the Adverse Event eCRF and reported to the Sponsor in accordance with instructions provided in this section and in Sections 5.4–5.6.

For each AE recorded on the Adverse Event eCRF, the investigator will make an assessment of seriousness (see Section 5.2.2 for seriousness criteria), severity (see Section 5.3.3), and causality (see Section 5.3.4).

5.3.1 Adverse Event Reporting Period

Investigators will seek information on AEs at each patient contact. All AEs, whether reported by the patient or noted by study personnel, will be recorded in the patient's medical record and on the Adverse Event eCRF.

After informed consent has been obtained but prior to initiation of study drug, only SAEs caused by a protocol-mandated intervention (e.g., invasive procedures such as LP) should be reported (see Section 5.4.2 for instructions for reporting SAEs).

After initiation of study drug, all adverse events will be reported until 5 months after the final dose of study drug.

Instructions for reporting AEs that occur after the AE reporting period are provided in Section 5.6.

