3.3 RATIONALE FOR STUDY DESIGN

3.3.1 Rationale for RO7234292 Dose and Schedule

Effective 22 March 2021 dosing in this study (BN40955) is paused. On 18 Mar 2021, the BN40423 iDMC recommended that dosing be stopped in the Phase III randomized controlled trial. Because the OLE is exploring the same dosing regimens (i.e., RO7234292 120 mg Q8W and Q16W) the Sponsor made a decision to pause dosing in the OLE until further data assessments can be conducted.

In this study, RO7234292 will be administered either Q8W (RO7234292 Q8W arm) or Q16W (RO7234292 Q16W arm) by IT injection. The dose and dosing regimen administered in this study was initially the same as the dose and dosing regimen selected for the Phase III Study BN40423, a double-blind, placebo-controlled study of RO7234292 administered Q4W and Q8W by IT injection over 25 months in patients with manifest HD. However, based on preliminary 9-month data from the open-label Study BN40697, the Phase III Study BN40423 was amended to replace the

120 mg Q4W regimen with a 120 mg Q16W regimen. The same change was made to this study.

Until completion of Phase III Study BN40423, the magnitude and duration of mHTT protein lowering that is required for clinical efficacy is unknown. Specifically, it is unknown whether acute mHTT protein lowering alone with full recovery of protein levels between dosing will be sufficient for clinical efficacy, or whether more sustained suppression of protein levels will be required for clinical efficacy. Data from transgenic animal models suggest that brain tissue lowering of mHTT protein in the range of 30%–60% is associated with beneficial effects on the disease phenotype, which corresponds to a trough CSF lowering range of 20%–40% based on a non-human primate PK/PD model.

Because of this uncertainty, 2 active dosing regimens will be used in this study: RO7234292 Q8W (RO7234292 Q8W arm) and RO7234292 Q16W (RO7234292 Q16W arm), by IT injection.

The 120-mg dose has been chosen for the Q8W dosing group based on the following:

- In the chronic toxicology study in cynomolgus monkeys, the no-observed-adverse-effect level was determined to be at least 35 mg/dose (the highest dose tested). Conservatively correcting for differences in CSF volume between cynomolgus monkeys (≤ 15 mL) and humans (≥ 150 mL) with a scaling factor of 10, the human equivalent dose corresponds to 350 mg, representing a 3-fold safety margin to the proposed 120-mg clinical dose.

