5.4 IMMEDIATE REPORTING REQUIREMENTS FROM INVESTIGATOR TO SPONSOR

Certain events require immediate reporting to allow the Sponsor to take appropriate measures to address potential new risks in a clinical trial. The investigator must report such events to the Sponsor immediately; under no circumstances should reporting take place more than 24 hours after the investigator learns of the event. The following is a list of events that the investigator must report to the Sponsor within 24 hours after learning of the event, regardless of relationship to study drug:

- Serious adverse events (defined in Section 5.2.2; see Section 5.4.2 for details on reporting requirements)
- Adverse events of special interest (defined in Section 5.2.3; see Section 5.4.2 for details on reporting requirements)
- Pregnancies (see Section 5.4.3 for details on reporting requirements)

The investigator must report new significant follow-up information for these events to the Sponsor immediately (i.e., no more than 24 hours after becoming aware of the information). New significant information includes the following:

- New signs or symptoms or a change in the diagnosis
- Significant new diagnostic test results
- Change in causality based on new information
- Change in the event's outcome, including recovery
- Additional narrative information on the clinical course of the event

Investigators must also comply with local requirements for reporting SAEs to the local HA and IRB/EC.

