5.4.2.2 Events That Occur after Study Drug Initiation

After initiation of study drug, SAEs and AESIs will be reported until 5 months after the final dose of study drug. Investigators should record all case details that can be gathered immediately (i.e., within 24 hours after learning of the event) on the Adverse Event eCRF and submit the report via the electronic data capture (EDC) system. A report will be generated and sent to Roche Safety Risk Management by the EDC system.

In the event that the EDC system is unavailable, the paper Clinical Trial Serious Adverse Event/Adverse Event of Special Interest Reporting Form provided to investigators should be completed and submitted to the Sponsor or its designee immediately (i.e., no more than 24 hours after learning of the event), either by faxing or by scanning and emailing the form using the fax number or e-mail address provided to investigators. Once the EDC system is available, all information will need to be entered and submitted via the EDC system.

Instructions for reporting SAEs that occur >5 months after the final dose of study treatment are provided in Section [5.6](#).

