5.6 ADVERSE EVENTS THAT OCCUR AFTER THE ADVERSE EVENT REPORTING PERIOD

The Sponsor should be notified if the investigator becomes aware of any SAE that occurs after the end of the AE reporting period (defined as 5 months after the final dose of study drug), if the event is believed to be related to prior study drug treatment. These events should be reported through use of the Adverse Event eCRF. However, if the EDC system is not available, the investigator should report these events directly to the Sponsor or its designee, either by faxing or by scanning and emailing the paper Clinical Trial Serious Adverse Event/Adverse Event of Special Interest Reporting Form using the fax number or e-mail address provided to investigators.

5.7 EXPEDITED REPORTING TO HEALTH AUTHORITIES, INVESTIGATORS, INSTITUTIONAL REVIEW BOARDS, AND ETHICS COMMITTEES

The Sponsor will promptly evaluate all SAEs and AESIs against cumulative product experience to identify and expeditiously communicate possible new safety findings to investigators, IRBs, ECs, and applicable HAs based on applicable legislation.

To determine reporting requirements for single AE cases, the Sponsor will assess the expectedness of these events using the following reference document:

- RO7234292 Investigator's Brochure

The Sponsor will compare the severity of each event and the cumulative event frequency reported for the study with the severity and frequency reported in the applicable reference document.

Reporting requirements will also be based on the investigator's assessment of causality and seriousness, with allowance for upgrading by the Sponsor as needed.

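### Adverse event reporting ends 5 months after a final dose that the protocol does not define for the dosing pause, so late off-drug events may have no clear reporting rule

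*Combined protocol and SAP*

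**What the plan says.** **The cap.** Section 5.3.1: "After initiation of study drug, all adverse events will be reported until 5 months after the final dose of study drug." Section 5.4.2.2 repeats it for serious adverse events (SAEs) and adverse events of special interest (AESIs): "After initiation of study drug, SAEs and AESIs will be reported until 5 months after the final dose of study drug." Footnote bb of Appendix 1a and footnote z of Appendix 1b attach the same limit to the adverse event row of the schedules.

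**After the cap.** Section 5.6 asks for notification of an SAE only "if the event is believed to be related to prior study drug treatment". The two footnotes add deaths from any cause.

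**Before the first dose.** Section 5.3.1: "only SAEs caused by a protocol-mandated intervention (e.g., invasive procedures such as LP) should be reported."

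**The pause.** Section 3.3.1: "the Sponsor made a decision to pause dosing in the OLE until further data assessments can be conducted." It takes effect on 22 March 2021. Section 3.1.1 keeps enrolled patients under safety and efficacy follow-up to study completion. Appendix 1a (footnote s), Appendix 1b (footnote u) and Appendix 2b give all of them an LP without drug every 16 weeks.

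**Text favouring continued capture.** Section 5.3.1: "Investigators will seek information on AEs at each patient contact." Its next sentence has all AEs entered in the medical record and on the Adverse Event eCRF. Section 5.2.2: "Serious adverse events are required to be reported by the investigator to the Sponsor immediately." Section 5.4 lists the events that the investigator "must report to the Sponsor within 24 hours after learning of the event, regardless of relationship to study drug". The schedules mark AEs at every clinic visit and call, at end of treatment (EoT) and at safety follow-up (SFU).

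The C-SSRS and EQ-5D-5L footnotes say that these assessments continue during the pause. The AE footnotes contain no such line.

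**The concern.** The reporting period hangs on an event, the final dose, that cannot be identified while dosing is suspended without an end date. Two sites could apply the same sentence differently. One would keep reporting because treatment has not ended. The other would count 5 months from the last dose given.

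Safety is the only objective in Section 2 not labelled exploratory, and AE incidence and severity is its first endpoint. Section 6.5 plans AE incidence by relationship to study drug or procedure. If sites stop at different points, off-drug incidence would be incomplete and not comparable between sites.

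Events from drug-free LPs are the clearest case. Section 5.2.1 counts events from mandated interventions as AEs, and LP-caused SAEs are expressly reportable before the first dose, but no matching rule covers the time after the window. Such events are not rare: Section 5.1.1 gives potential LP-associated AEs in 22.9% (Q8W) and 15.1% (Q16W) of patients in this study by 7 August 2020. Those figures predate the pause, so they show only the order of frequency.

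**Working it through.** No sample size or error rate is involved. The check compares passages and dates.

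**1. Is the final dose defined for the pause?** No passage does so.
- Section 5.1.3.2 treats interruption separately from permanent discontinuation (Section 4.6.1).
- Section 4.6.1 places the EoT and SFU visits after the final dose, and footnote c of Appendix 1a times EoT from the decision to discontinue. Both suggest that a paused patient has not yet had a final dose.
- Nothing states this, and nothing says what follows if dosing never resumes. The last pre-pause dose is then the final dose in retrospect.

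**2. When would the window close if the last pre-pause dose is final?** Close = last dose + 5 calendar months (150 to 153 days).
- Dose on 22 March 2021: closes 22 August 2021 (153 days). This is the latest possible date.
- Q8W dose 8 weeks earlier, 25 January 2021: closes 25 June 2021 (151 days).
- Q16W dose 16 weeks earlier, 30 November 2020: closes 30 April 2021 (151 days).

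**3. Which drug-free LPs fall inside?** From Appendix 2b, LPs fall 16, 32, 48... weeks after the last dose for Q16W patients and for Q8W patients last dosed at an LP week. They fall 8, 24, 40... weeks after it for Q8W patients last dosed at a non-LP week.
- First LP: 8 × 7 = 56 or 16 × 7 = 112 days, both under 150, so inside.
- Second LP: 24 × 7 = 168 or 32 × 7 = 224 days, both over 153, so outside.
- With the ±1-week window on both dose and LP, the first is at most 112 + 14 = 126 days (inside) and the second at least 168 − 14 = 154 days (outside by one day).
- The split is not absolute. Sections 3.1.1 and 4.5.5 allow a repeat dosing attempt up to 7 days later. A dose attempt at +7 days, a repeat at +14 and an LP at −7 give 168 − 21 = 147 days, so a second LP can fall inside. A missed dose can push even the first LP outside.

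The documents do not say how long off-drug follow-up lasts, so totals are scenarios on the nominal schedule. Assuming 26 weeks since the last dose, 0 of 1 or 1 of 2 LPs are outside; 52 weeks, 2 of 3; 96 weeks, 5 of 6.

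**4. EoT and SFU visits.** EoT is 4 weeks after the decision to discontinue and SFU 20 weeks after EoT. Let t be the days from last dose to decision.
- EoT is at t + 28, outside a 153-day window once t exceeds 153 − 28 = 125 days.
- SFU is at t + 28 + 140 = t + 168. With both visit windows at their earliest it is at t + 21 + 133 = t + 154. It is outside even when t = 0, yet the schedule marks AEs there.

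**5. What remains reportable after the window?** Drug-related SAEs (Section 5.6) and, under the footnotes, all deaths. Table 4 makes related the default attribution, which widens the first group. Non-serious AEs and non-fatal SAEs not attributed to the drug have no clear rule. Sections 5.2.2 and 5.4 state the SAE duty without a time limit but refer to Section 5.4.2 for how to report, and that section contains the cap.

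**The case against.** The strongest reply is that the protocol already implies the answer. Dosing is paused, not ended. A patient who has not discontinued stays in the treatment-period column, where AEs are marked at every visit and call. Section 5.3.1 requires all AEs to be recorded on the eCRF, the evident source for the Section 6.5 tables. New or worsened clinically significant abnormalities on neurologic examination (Section 4.5.3), physical examination and vital signs (schedule footnotes) go on the Adverse Event eCRF with no 5-month limit. Section 5.5.1 asks for follow-up of SAEs related to trial procedures.

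Most of this stands, and it makes the open window the better-supported reading while dosing is only paused. Three gaps remain. The recording sentence sits in the same section as the cap, under a heading about the reporting period. The examination rules do not cover symptoms such as headache or procedural pain. And the argument lapses if the pause becomes permanent, a realistic prospect given that the monitoring committee recommended permanent cessation in the parent trial (Section 1.3).

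A reader might infer that AE reporting stops in August 2021, or that the protocol excludes harm from drug-free LPs. The documents do not support that: no passage equates the last pre-pause dose with the final dose, and several point to continued capture.

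A reader might also want a fixed share of off-drug time that goes unreported. That share depends on an assumed last-enrolment date. With last enrolment on 22 March 2021 and the 6-month minimum of Section 3.2, the study ends on 22 September 2021, and a patient dosed on 22 March has 31 of 184 days (17%) outside. With last enrolment a month earlier, the minimum end is 22 August 2021 and the same patient has 0 of 153. No such percentage should be relied on.

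**Conclusion.** The point holds as an ambiguity that should be fixed. It does not show that reporting has ceased. Under an open window nothing is lost. If the last pre-pause dose is treated as final, or becomes final because dosing never resumes, the window closes between 30 April and 22 August 2021 for patients dosed on schedule. Non-serious AEs and non-fatal SAEs not attributed to the drug then lack a clear reporting rule. On the nominal schedule this affects every drug-free LP after the first. It also affects the SFU visit in every case, and the EoT visit when the decision to discontinue comes more than about 4 months after the last dose.

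The loss would be partial. Drug-related SAEs and deaths stay reportable, AEs are still sought at each contact, and examinations, laboratory tests, C-SSRS, MoCA and MRI continue. Confidence is high that the definition is missing. How much data would be affected depends on how sites read the text and how long the pause lasts, and the documents give neither.

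**What to change.** In Sections 5.3.1, 5.4.2.2 and 5.6, footnote bb of Appendix 1a and footnote z of Appendix 1b, state that AEs, SAEs and AESIs are recorded and reported until the later of 5 months after the last dose received and the patient's last study visit, including SFU. Say that this applies whether or not dosing is paused and covers events caused by LPs done without drug. Naming the last dose received removes the dependence on whether the pause has ended.

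The cost is protocol wording, eCRF guidance and some extra AE data entry for off-drug patients, who are already asked about AEs at every visit and call.

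A separate minor repair, not caused by the pause: Section 5.3.5.8 sends deaths after the reporting period to Section 5.6, which names only drug-related SAEs, while footnotes bb and z ask for all deaths. These passages should be reconciled.
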